#### 6.4. VISIT WINDOWS

There will be no derivation for visit windows in terms of summary of assessments. Nominal visits as indicated in [Table 1](#) will be used for TLFs.

#### 6.5. POOLING OF CENTERS

There will be no pooling of centers.

#### 6.6. SUBGROUPS

Subgroup analyses will be conducted on the co-primary efficacy endpoints and will be exploratory in nature. The following categories will be evaluated in the subgroup analyses:

- Age (18-34 years, 35-49 years, 50-64, and  $\geq 65$  years)
- Gender (male and female)
- Ethnicity (Hispanic and non-Hispanic)

Subgroup analyses of efficacy are described in Section 8.3. Additional subgroup analyses based on baseline information may be performed. These analyses will be data driven, exploratory, and described in the Clinical Study Report if conducted.

## 7. DEMOGRAPHIC, OTHER BASELINE CHARACTERISTICS AND MEDICATION

### 7.1. SUBJECT DISPOSITION AND WITHDRAWALS

Subject disposition will be presented for the Screened Set, and will include the following:

- The number of subjects screened
- The number (%) of subjects who failed screening
- The number (%) of subjects randomized into DB1
- The number of subjects re-randomized into DB2
- The number (%) of subjects in the FAS1
- The number (%) of subjects in the FAS2
- The number (%) of subjects in the SS
- The number (%) of subjects in the SS1
- The number (%) of subjects in the SS2
- The number (%) of subjects in the PPS
- The number (%) of subjects who completed DB1
- The number (%) of subjects who completed DB2
- The number (%) of subjects who completed the study
- The number (%) of subjects who discontinued from DB1 and the primary reason for discontinuation
- The number (%) of subjects who discontinued from DB2 and the primary reason for discontinuation
- The total number (%) of subjects who discontinued from the study and the primary reason for discontinuation

The summary will be performed for the Screened Set, as well as for the DB1 and DB2 treatment periods. The denominators for the percentage calculation will be listed in the footnote of subject disposition table.. No statistical testing will be performed on these data.

Subjects' completion/discontinuation status will be listed, including subject identifier, date of completion/early discontinuation and, for those who discontinued early, the specific reason(s) for discontinuation.

The inclusion/exclusion criteria for the subjects who fail screening will be listed.

## 7.2. DEMOGRAPHIC AND OTHER BASELINE CHARACTERISTICS

Demographics and other baseline characteristics will be summarized for the SS, SS1, and SS2 by treatment group and overall, with descriptive statistics including n, mean, standard deviation, median, minimum, and maximum for numeric variables and frequency and percentage for categorical variables. Demographics include age, gender, childbearing potential for females, ethnicity, race, height, weight, smoking history, and BMI.

BMI will be calculated as follows:

$$\text{BMI (kg/m}^2\text{)} = \text{Weight (kg)}/[\text{Height(m)}^2].$$

All collected demographics and baseline characteristics will be listed.

## 7.3. MIGRAINE HISTORY

All migraine history data will be summarized descriptively by treatment group and overall for the SS, SS1, and SS2.

All collected migraine history data will be listed.

## 7.4. MEDICAL HISTORY AND CONCOMITANT DISEASES

A summary table of the number and percentage of subjects by medical history system organ class (SOC) and preferred term (PT) will be produced for subjects in the SS. Previous and concurrent diseases/conditions will be sorted alphabetically by SOC and PT using the Medical Dictionary for Regulatory Activities (MedDRA) coding dictionary, version 19.0 or higher. For the summary tables, a subject may appear more than once if he/she has more than one medical history coded under different SOC categories. However, the subject will be counted only once in the overall category.

A separate by-subject listing for medical history data will also be provided. Surgical history including procedure, date of surgery, and reason for surgery will be listed.

## 7.5. MEDICATION

### 7.5.1. Study Drug Accountability

All data in the study drug accountability log will be listed, which will include the dates and kit number(s) of the drug dispensed and returned.

### 7.5.2. Prior and Concomitant Medications

All prior and concomitant medications will be classified using the Anatomical Therapeutic Chemical (ATC) classification and preferred drug names from the World Health Organization Drug Dictionary (WHO-DD), version March 2016.

Summaries of medications will be presented in tabular form using the highest level ATC term as an upper classification and the preferred drug name as a lower classification level. All medications will be summarized by treatment group and overall and sorted by descending counts in the upper classification term and the lower classification term within the upper. The summary will consist of the frequency and percentage of subjects who used the medication at least once. For each subject, the medication will be counted only once within the upper classification level and only once within the lower classification level.

Medications will be considered prior if stopped before the DB1 dose date. Medications with a start or stop date on or after the DB treatment period dosing date will be considered concomitant medications. If a concomitant medication starts on or after the start time of DB1 dose administration, it is considered a concomitant medication to the study treatment in DB1, but not in DB2. If a concomitant medication starts on or after the start time of DB2 dose administration, it is considered a concomitant medication to the study treatment in DB2. All medications marked as ongoing are concomitant medications. A medication with an incomplete start/stop date will have its date imputed as described in SAP Section 6.3 solely to determine if the medication is prior or concomitant.

Summaries of prior and of concomitant medications will be presented separately in tables and will be based on the SS. Prior and concomitant medications will be listed by subject. An identifier will be included to show if a medication is prior or if it is concomitant with respect to the applicable DB treatment period.

## 8. EFFICACY

### 8.1. CO-PRIMARY EFFICACY ENDPOINTS AND ANALYSES

#### 8.1.1. Primary Analyses of the Co-Primary Endpoints

The first co-primary efficacy endpoint is the proportion of subjects who are pain-free 2 hours postdose compared between DFN-15 and placebo in the DB1 treatment period (defined as a reduction from predose moderate [Grade 2] or severe [Grade 3] pain to none [Grade 0]).

The second co-primary efficacy endpoint is the proportion of subjects who are free from their Screening MBS among nausea, photophobia, and phonophobia at 2 hours postdose compared between DFN-15 and placebo in the DB1 treatment period. A subject's Screening MBS is obtained at Screening via Migraine History assessment, and for the analysis of the co-primary endpoint that Screening MBS symptom must be present at predose but it does not have to be designated as the MBS at predose.

To test for statistical significance of the co-primary efficacy endpoints, the closed sequential testing procedure will be utilized. If the first co-primary endpoint is statistically significant at a two-sided 0.05 level of significance, the second co-primary endpoint will be tested at a two-sided 0.05 level of significance. The study must show a significant statistical beneficial experimental treatment effect for both co-primary endpoints to be considered statistically successful, controlling the significance level at 0.05. Since statistical significance with both co-primary endpoints is required to declare trial success, multiplicity due to multiple primary endpoints is a non-issue.

The first co-primary efficacy endpoint will be analyzed using Fisher's exact test. Following the closed sequential procedure, the second co-primary efficacy endpoint will be analyzed using Fisher's exact test if the first co-primary endpoint is statistically significant.

The proportion of subjects who are pain-free at 2 hours postdose will be calculated as the number of subjects who are pain-free at 2 hours postdose divided by the number of subjects with non-missing assessment at 2 hours postdose. Missing primary efficacy endpoint data will be imputed using the last observation carried forward (LOCF). Results based on the LOCF data and the observed data will be displayed separately.

The number of subjects with response, the number of subjects with non-missing assessment, proportions for the DFN-15 and placebo groups, 95% exact CIs for those proportions, the odds ratio for response, and the corresponding p-value will be presented for the comparison between two treatment groups for the FAS1. This analysis will exclude subjects who took rescue medication prior to the data collection of the 2 hours postdose time point (inclusive; LOCF), as well as subjects who have predose pain level = mild (Grade 1) or none (Grade 0). The analysis will also be performed using the PPS.

If the first co-primary efficacy endpoint is statistically significant, results will be found similarly for the second co-primary efficacy endpoint.

If statistical significance ( $p < 0.05$ ) is not achieved for either study 006 or study 007 (or both studies) co-primary endpoints, additional analyses will be conducted. Detailed information will be included in a separated Statistical Analysis Plan.

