### 8.3. EXPLORATORY ANALYSES

Exploratory analysis will be conducted for the proportion of subjects who are pain-free 2 hours postdose compared between DFN-15 and placebo in the DB1 treatment period with different predose pain grades (Moderate [Grade 2] or Severe [Grade 3]), respectively. The proportion of subjects who are pain-free at 15, 30, and 45 minutes and 1, 1.5, 2 (DB2 period), 4, and 24 hours postdose will also be compared between DFN-15 and placebo: during DB1 treatment period, predose severity = Moderate or Severe; during DB2 treatment period, predose severity = Mild, Moderate or Severe. The corresponding p-values from Fisher's exact test will be computed for the comparison between treatment groups.

Exploratory analysis will also be conducted for the proportion of subjects with their predose MBS among nausea, photophobia and phonophobia absent at 15, 30, and 45 minutes and 1, 1.5, 2, 4, and 24 hours postdose during each DB treatment period. The corresponding p-values from Fisher's exact test will be computed for the comparison between treatment groups for the FAS1 and FAS2. A subject's predose MBS is obtained from eDiary.

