### 8.4. SUBGROUP ANALYSES

Exploratory subgroup analyses on the co-primary endpoints will be conducted using the following baseline categories for the FAS1:

- Age (18-34 years, 35-49 years, 50-64 and >=65 years)
- Gender (male and female)
- Ethnicity (Hispanic and non-Hispanic)

For each subgroup, the odds ratio for response and the 95% CI for the odds ratio for each of the co-primary endpoints will be calculated using the treatment group, the subgroup variable, and the treatment-by-subgroup interaction term as covariates in the logistic regression model. Since the results of these subgroup analyses are exploratory, future studies can examine the treatment effect among the subgroup covariates that have a significant treatment-by-subgroup interaction term.

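### Both co-primary tests are unadjusted Fisher's exact tests, valid but conservative at this size, and the primary table has no confidence interval for the treatment effect

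*SAP*

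**What the plan says.** SAP 8.1.1 states for pain freedom at 2 hours: "The first co-primary efficacy endpoint will be analyzed using Fisher's exact test". For the Screening MBS endpoint it states that "the second co-primary efficacy endpoint will be analyzed using Fisher's exact test if the first co-primary endpoint is statistically significant". Protocol 10.5.1 names the same test for both endpoints. Neither document gives a covariate or stratum for these tests, and neither states a stratification factor for the randomization (protocol 8.1.2, SAP 3.6).

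Besides counts and arm proportions, the primary table is to hold "95% exact CIs for those proportions, the odds ratio for response, and the corresponding p-value". The intervals belong to the single-arm proportions. No interval is listed for the odds ratio, and no risk difference is listed. The sensitivity analyses in SAP 8.1.2 likewise list only per-arm intervals and p-values. An interval for an effect appears only in the exploratory subgroup models of SAP 8.4, where "the odds ratio for response and the 95% CI for the odds ratio for each of the co-primary endpoints will be calculated".

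SAP 8.1.1 also removes subjects whose predose pain was mild or absent, so the analysed subjects had moderate or severe pain. The SAP uses that grade in 8.3, where pain freedom at 2 hours is compared "with different predose pain grades (Moderate [Grade 2] or Severe [Grade 3]), respectively", as an exploratory analysis.

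The sample size sections (protocol 10.7, SAP 3.5) state 88% power for pain freedom with 600 subjects and 94% for MBS freedom with 480, each with 15% dropout.

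**The concern.** Pain freedom sets the sample size and is the gate to the second co-primary, so power lost there is power lost for trial success. Nothing in the documents explains why an exact test is needed with roughly 45 to 75 expected responders per arm. The predose grade is already collected, and it is part of the endpoint definition, yet the confirmatory test does not use it.

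The other half is reporting. As written, a Phase 3 trial would publish its main effect as an odds ratio without an interval, while its exploratory subgroups would have intervals.

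**Working it through.** **Inputs from the documents.** Pain-free rates 17.6% (placebo) and 29.2% (DFN-15); MBS-free rates 28.2% and 44.7%; N = 600 and 480; dropout 15%; two-sided alpha 0.05 (protocol 10.7, SAP 3.5, SAP 6.1.1). Evaluable per arm: 600/2 × 0.85 = 255 and 480/2 × 0.85 = 204.

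**Reproducing the stated power.** Normal approximation with pooled variance under the null:

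power = Φ{[d − 1.96·√(2p̄(1−p̄)/n)] / √[(p₁(1−p₁) + p₂(1−p₂))/n]}

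- Pain freedom, n = 255: d = 0.116, p̄ = 0.234; (0.116 − 1.96 × 0.03750)/0.03714 = 1.145, so 87.4%.
- MBS freedom, n = 204: d = 0.165, p̄ = 0.3645; (0.165 − 1.96 × 0.04765)/0.04695 = 1.525, so 93.6%.
- Taking dropout as N/1.15 instead gives 88.1% and 94.1%.

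The stated 88% and 94% are therefore chi-square-type figures.

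**Power of the planned test.** I enumerated all pairs of binomial outcomes and applied the two-sided test at 0.05.

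| Pain freedom, 255 per arm | Fisher | Pearson chi-square |
|---|---|---|
| Power, 17.6% vs 29.2% | 85.5% | 87.6% |
| Type I error, common rate 17.6% to 29.2% | 3.9% to 4.0% | 5.0% |

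Fisher's test needs 272 evaluable per arm to reach 87.6%. That is 17 more per arm, or 2 × 17/0.85 = 40 more randomized subjects. For MBS freedom, Fisher power is 92.2% at 204 per arm and 96.7% at 255.

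**What stratifying adds for pain freedom.** The documents give neither the share of severe attacks nor how strongly severity predicts response, so both are assumed: 30% or 50% severe, and a moderate-versus-severe odds ratio for pain freedom of 1 to 4. The marginal rates are held at 17.6% and 29.2%, with 255 per arm and 40,000 simulated trials per scenario. Each cell gives the 30% severe value, then the 50% severe value.

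| Assumed odds ratio | Fisher | Chi-square | Cochran-Mantel-Haenszel | Stratified minus chi-square (points) |
|---|---|---|---|---|
| 1 | 85.6 / 85.5 | 87.8 / 87.7 | 87.6 / 87.6 | −0.2 / −0.1 |
| 2 | 85.3 / 85.3 | 87.5 / 87.4 | 87.9 / 88.2 | 0.4 / 0.7 |
| 3 | 85.6 / 85.2 | 87.7 / 87.4 | 88.5 / 88.9 | 0.8 / 1.4 |
| 4 | 85.6 / 85.3 | 87.7 / 87.5 | 89.1 / 89.7 | 1.5 / 2.2 |

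Differences are taken before rounding. The simulation error of one power value is about √(0.877 × 0.123/40,000) = 0.16 points. Type I error of the stratified test stays between 4.9% and 5.1%.

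**The intervals the table omits.** These are Wald 95% intervals at the planning rates. Risk difference: d ± 1.96·√[p₁(1−p₁)/n + p₂(1−p₂)/n]. Log odds ratio: standard error √(sum of reciprocal expected cell counts).

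- Pain freedom, 255 per arm: 11.6 ± 1.96 × 3.714 = 4.3 to 18.9 points. Odds ratio (0.292 × 0.824)/(0.176 × 0.708) = 1.93; standard error of its log 0.2145; interval 1.27 to 2.94.
- MBS freedom, 204 per arm: 16.5 points, interval 7.3 to 25.7; odds ratio 2.06, interval 1.36 to 3.11.

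**The case against.** The plan has a fair defence. An unadjusted Fisher's test keeps type I error below 0.05, is prespecified in both documents, and suits a 1:1 randomization with no stated strata. Severity is not ignored across the SAP, since 8.3 examines it. Power of 85.5% is still respectable. All of this stands, and it makes the point one of efficiency and reporting.

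Four stronger readings are tempting, and the documents do not support them.

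- *Leaving severity out is what costs the power.* Most of the dependable gain, about 2 points, comes from leaving Fisher's test. Stratifying adds nothing if severity is not prognostic, and the SAP's exploratory analysis by grade is no evidence that it is.
- *Both co-primaries gain power.* Nothing in the documents shows that pain severity predicts MBS freedom, and power there is already above 90%.
- *The trial could not state the precision of its effect.* The table gives responders and denominators for each arm, so a crude interval can be derived from it. The table shells, which are not in these documents, may add detail. The gap is that the plan does not commit to an interval or its method.
- *Changing the test has no downside.* A stratified odds ratio is conditional and differs from the crude one now planned. The test would depart from protocol 10.5.1. It would also rest on the moderate/severe grade, and protocol 9.2.1.2 lets predose assessments be entered retrospectively when a subject did not follow instructions. A grade entered after dosing could be coloured by response. Nor is a rule stated for a missing predose grade.

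**Conclusion.** The point holds as a matter of efficiency and reporting. The missing effect interval is the firmer half: it rests on the text alone and applies to both co-primaries.

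For pain freedom, the planned test has 85.5% power against the stated 88%, with an actual type I error of about 4%. These figures rest on the plan's own rates and 255 evaluable per arm. About 2 points come back with a less conservative test. A further 0 to about 2 points from stratifying rests wholly on the assumed severity mix and odds ratio of 1 to 4. The change is worth making, but the trial is valid without it.

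**What to change.** Before unblinding, amend SAP 8.1.1 to:

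- name one primary test for both co-primaries, the Cochran-Mantel-Haenszel test stratified by predose pain severity (moderate or severe);
- report the stratum-adjusted risk difference and the odds ratio, each with a 95% confidence interval, and say that the stratified odds ratio is conditional;
- state how a missing predose grade is handled, and list which grades were entered retrospectively;
- keep Fisher's exact test as a sensitivity analysis;
- record the departure from protocol 10.5.1 in SAP Section 11.

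If the sponsor prefers to keep Fisher's test as primary, it should still add the two effect intervals and restate the power for that test as 85.5%.

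The cost is SAP wording, one program and the Section 11 entry, with no new data. The price is the departure from the protocol and the reliance on the predose grade.

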During the 2 treatment periods of the study, subjects will have an option, if required, to take rescue medication after the 2 hours postdose time point efficacy data have been recorded in the eDiary. Rescue medication will be decided between the Investigator and the subject, exclusive of study prohibited medications. Rescue medication will not be provided by the Sponsor, and its use should be managed by the subject and their Investigator.

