### **8.5.2 *Rescue Medication***

When a subject gets a migraine attack, the study drug should not be taken if the subject has treated an episodic migraine attack acutely with any other medication within the past 48 hours, or if the subject has used an analgesic for non-migraine pain acutely within the past 48 hours.

If a subject does not experience sufficient or any pain relief from the study drug, he/she may take rescue medication, if needed, after 2 hours or more after taking the study drug, and only after completing the 2 hours postdose assessments in the eDiary. The specific rescue medication will initially be decided between the Investigator and the subject before or at V2, but may be adjusted as needed during the treatment period, with the Investigator ensuring that prohibited medications ([Section 8.5.3](#)) are not assigned and consulting with the Medical Monitor, if needed. Rescue medication will not be provided by the Sponsor, and its use should be managed by the subject and their Investigator. Rescue medication related decisions should be detailed in the source documents.

Rescue medication, including NSAIDs or other migraine medications, prescription or non-prescription drugs, vitamins, herbal, and dietary supplements (including St John's Wort), should be taken as described above. Subjects should not take prohibited medications listed in [Section 8.5.3](#) as a rescue medication.

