## 10.5 Methods of Analysis

### 10.5.1 Primary Efficacy Analysis

Efficacy analyses for the co-primary and secondary endpoints will be based on the FAS population.

The first co-primary efficacy endpoint of the proportion of subjects who are free from headache pain at 2 hours after the first dose of study drug taken for a migraine attack with moderate to severe headache pain during the DB1 period, will be analyzed using Fisher's exact test. The

second co-primary efficacy endpoint of the proportion of subjects who are free from their Screening MBS among nausea, photophobia, and phonophobia at 2 hours postdose during the DB1 period will be similarly analyzed using Fisher's exact test. A subject's MBS will be obtained at Screening via Migraine History assessment and, for the analysis of the co-primary endpoint, that symptom must be present predose but does not have to be designated as the MBS at predose.

Analyses will be performed using the last observation carried forward (LOCF) and observed data in the FAS population and PP population.

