#### **10.7 Determination of Sample Size**

Approximately 600 subjects will be randomized for the DB1 period. Subjects who discontinue participation without completing the study protocol will not be replaced.

The first co-primary endpoint is the comparison of the proportion of subjects who are pain-free at 2 hours after the first dose of study drug. It is assumed that 17.6% of placebo and 29.2% of DFN-15 (treated) subjects will be pain-free at 2 hours. A sample size of 600 subjects will provide 88% power to detect this assumed difference between placebo and DFN-15 at a 5% (2-sided) level of significance and with a 15% dropout rate.

The second co-primary endpoint is the comparison of the proportion of subjects who are free from their Screening MBS among nausea, photophobia, and phonophobia at 2 hours after the first dose of study drug. It is assumed that 28.2% of placebo and 44.7% of DFN-15 (treated) subjects will be free from their Screening MBS at 2 hours. A sample size of 480 subjects will provide 94% power to detect this assumed difference between placebo and DFN-15 at a 5% (2-sided) level of significance and with a 15% dropout rate.

Since the sample size for the first co-primary endpoint is larger than that of the second co-primary endpoint, the larger sample size will be used for the study.

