#### **8.1.2. Sensitivity Analyses of the Co-Primary Endpoints**

Besides the scenario with the observed missing data for the co-primary efficacy endpoints, two additional scenarios will be considered for each of the co-primary endpoints.

For the first co-primary endpoint, in one scenario, subjects with missing headache pain assessments at 2 hours postdose will be assigned as having a pain level of 3 (severe) at 2 hours postdose; that is, they will be assigned as having severe headache pain at 2 hours postdose. In another scenario, subjects with missing headache pain assessments at 2 hours postdose will be assigned as having a pain level of 0 (None) at 2 hours postdose; that is, they will be assigned as having headache pain freedom at 2 hours postdose.

For the second co-primary endpoint, in one scenario, subjects with a missing response for MBS status will be assigned as being free from their MBS. In another scenario, subjects with a missing response for MBS status will be assigned as not being free from their MBS.

For the first co-primary endpoint, proportions of subjects pain-free at 2 hours postdose for the DFN-15 and placebo groups, 95% exact CIs for those proportions, and the corresponding p-value from Fisher's exact test for the three scenarios will be presented. A similar analysis will be conducted for the proportion of subjects who are free from their MBS at 2 hours postdose.

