### **8.2. SECONDARY ENDPOINTS AND ANALYSES**

The secondary endpoints that involve proportions of subjects who have a response will be summarized by treatment group and will be analyzed using the LOCF for missing secondary efficacy endpoint data.

Secondary endpoint analyses will be conducted as indicated for the FAS1 and FAS2 and will exclude subjects who took rescue medication prior to the data collection of the 2

hours postdose time point (inclusive; LOCF). For all secondary endpoint analyses in DB1 for the FAS1, subjects who have predose pain level = mild (Grade 1) or none (Grade 0) will also be excluded. For all secondary endpoint analyses in DB2 for the FAS2, subjects who have predose pain level = none (Grade 0) will also be excluded.

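### The co-primary analyses drop subjects who took rescue up to the 2-hour assessment, and no planned analysis counts them as a group as non-responders; the effect depends on an early-rescue rate the documents do not give

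*SAP*

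**What the plan says.** Protocol 10.5.1 sets the population: "Efficacy analyses for the co-primary and secondary endpoints will be based on the FAS population". It mentions no exclusion for rescue. SAP 8.1.1 adds one for the FAS1 analysis: "This analysis will exclude subjects who took rescue medication prior to the data collection of the 2 hours postdose time point (inclusive; LOCF"). The same section handles the second co-primary in the same way. SAP section 11 lists the exclusion as a change from the protocol, but its parenthesis has only the word inclusive, without LOCF.

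The protocol ties rescue to lack of benefit. Section 8.5.2 says: "If a subject does not experience sufficient or any pain relief from the study drug, he/she may take rescue medication". It also sets the timing: section 5.1 lets subjects "take rescue medication after the 2 hours postdose time point efficacy data have been recorded in the eDiary". Rescue before that entry is therefore a departure from the protocol.

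Other relevant provisions:
- SAP 8.1.2 acts on missing values only. In one scenario, "subjects with missing headache pain assessments at 2 hours postdose will be assigned as having a pain level of 3 (severe"). Rescue is not mentioned.
- SAP 5.5 makes the per-protocol set a subset of FAS1.
- SAP 8.2 repeats the exclusion for the secondary endpoints, which "will exclude subjects who took rescue medication prior to the data collection of the 2" hours time point.
- SAP 8.2.13 and 9.2 count rescue from 2 to 24 hours only.
- SAP 8.2.11 and 8.2.12 treat rescue at 2-24 hours as failure of sustained relief and sustained freedom.

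**The concern.** Early rescue happens after randomization and can be affected by treatment. Removing early rescuers from numerator and denominator means the two arms are no longer compared as randomized. The estimate then mixes the effect on response with the effect on early rescue. A subject who gives up on study drug before 2 hours is naturally a treatment failure, and the SAP already takes that view of rescue in its sustained endpoints. In the co-primary analyses the same subject disappears.

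Both co-primaries carry the trial: "The study must show a significant statistical beneficial experimental treatment effect for both co-primary endpoints to be considered statistically successful". The result should not depend on an unreported count of early rescuers, and no planned analysis would show how far it does.

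**Working it through.** **Is there any planned analysis that counts early rescuers as non-responders?**
- *Main analysis.* If the LOCF tag only clarifies the time point, early rescuers are out of both the LOCF and the observed runs. If it limits the exclusion to the LOCF run, the observed run uses their recorded scores, so a pain-free score after rescue counts as success. Neither is non-response.
- *8.1.2 scenarios.* The SAP does not say whether the exclusion carries over. If it does not, an early rescuer with a missing 2-hour value fails in the worst case and succeeds in the best case. One with a recorded score keeps it. The group as a whole is never coded as failure.
- *Per-protocol set.* A subset of FAS1 cannot restore subjects under the same rule.
- *Secondary endpoints.* 8.2 removes early rescuers before the sustained endpoints are scored.

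**Inputs (protocol 10.7, repeated in SAP 3.5).** Two-sided 0.05; 15% dropout. Pain freedom 29.2% vs 17.6%, 600 subjects, so 300 × 0.85 = 255 per arm. MBS freedom 44.7% vs 28.2%, 480 subjects, so 240 × 0.85 = 204 per arm: "A sample size of 480 subjects will provide 94% power to detect this assumed difference between placebo and DFN-15".

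**Stated power.** Pooled normal approximation: z = [d√n − 1.96√(2p̄q̄)] / √(p₁q₁ + p₀q₀).
- Pain freedom: (1.852 − 1.173)/0.593 = 1.145, power 87.4% (stated 88%).
- MBS: (2.357 − 1.334)/0.671 = 1.525, power 93.6% (stated 94%).
- Exact enumeration of the planned Fisher test: 85.5% and 92.2%. These are the baselines below.

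**Effect of the exclusion.** Let p be the response rate with early rescuers counted as non-responders, and r the early-rescue share. The exclusion estimates p/(1 − r) in each arm from n(1 − r) subjects. The difference changes by p₁r₁/(1 − r₁) − p₀r₀/(1 − r₀). This is zero when the placebo odds of early rescue are p₁/p₀ times the DFN-15 odds: 29.2/17.6 = 1.66 for pain freedom and 44.7/28.2 = 1.59 for MBS. Above that ratio the difference shrinks; below it, including at equal shares, it grows.

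All shares are assumptions, written DFN-15/placebo.

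| Early rescue | Pain freedom after exclusion | Difference (points) | Fisher power | MBS difference (points) | Fisher power |
|---|---|---|---|---|---|
| none | 29.2% vs 17.6% | 11.6 | 85.5% | 16.5 | 92.2% |
| 2%/4% | 29.8% vs 18.3% | 11.5 | 83.2% | 16.2 | 91.1% |
| 4%/2% | 30.4% vs 18.0% | 12.5 | 89.8% | 17.8 | 95.3% |
| 5%/10% | 30.7% vs 19.6% | 11.2 | 78.9% | 15.7 | 87.5% |
| 10%/5% | 32.4% vs 18.5% | 13.9 | 93.1% | 20.0 | 97.7% |

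**Under the null.** With pain freedom at an assumed 20% in both arms, the chance of a significant result favouring DFN-15 is 1.97% with no early rescue, 1.94% at 5%/5% and 1.93% at 10%/10%. Equal shares do no harm.

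**If the planned rates are instead post-exclusion rates.** Non-response coding then multiplies each rate by (1 − r) and keeps 255 per arm. Pain-freedom power at 5%/5% is 83.0%, against 83.5% with the exclusion. At 10%/5% it is 71.9% against 83.4%; at 5%/10% it is 88.9% against 84.0%.

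**The case against.** *The rule may rarely bite.* Rescue before the 2-hour entry is a deviation and no rate is documented. At 2%/4% or 4%/2%, about 5 and 10 subjects per arm, the pain-freedom difference moves by at most 0.9 point. This stands and limits the size of the point.

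*The exclusion probably works against the sponsor.* If rescue follows poor relief and DFN-15 works, early rescue should be commoner on placebo. If DFN-15 does nothing, shares should be about equal and the null is unharmed. A reader might infer that the exclusion inflates the DFN-15 effect; the documents do not support that, because they fix neither the rate nor the direction.

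*Early rescue is not hidden.* SAP 5.6 lists all deviations by subject. SAP 7.5.2 treats medication started after the DB1 dose as concomitant to DB1 and lists it by subject. A reader might infer that the balance could never be seen. That goes too far: it could be traced from the listings, though no planned table shows it by arm.

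*There is no protocol violation.* Protocol 10.1 lets the SAP supersede it, and section 11 discloses the change. That is correct, but disclosure does not replace an analysis that keeps these subjects.

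*Some early rescuers may fail in the 8.1.2 worst case.* True if the exclusion does not carry over and the 2-hour value is missing, but not for the group.

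**Conclusion.** The point holds as an inexpensive improvement that should be made, with medium confidence. The co-primary analyses condition on an event after dosing, and on either reading of the LOCF tag no planned analysis counts early rescuers as a group as non-responders.

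The size is unknown. Over the assumed pairs shown, the pain-freedom difference ranges from 11.2 to 13.9 points around the planned 11.6, and power from 78.9% to 93.1% around 85.5%. The larger shifts need 5% to 10% early rescue with a twofold imbalance. The calculation takes the planned rates as rates with early rescuers counted as failures.

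Two further readings are not supported. One is a figure for power or false success on both co-primaries together. That needs the share of subjects evaluable for MBS and the correlation between endpoints, and neither is given; the 480 is a separate sample-size figure, not an MBS-evaluable count. The other is a quantified bias at 4 and 24 hours: handling of rescue after 2 hours at those time points is a separate question, and no rates are given for it.

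**What to change.** In SAP 8.1.1, keep in the denominator all FAS1 subjects with moderate or severe predose pain and, for MBS, with the Screening MBS present predose. Code acute migraine medication taken before the 2-hour assessment is recorded as non-response for both co-primaries, in the LOCF and observed analyses.

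In 8.1.2, keep the present exclusion as a sensitivity analysis and state how early rescuers enter the missing-data scenarios. Add a table of early rescue by arm.

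In 8.2, apply the same coding to the 2-hour and sustained responder endpoints. Use one wording in 8.1.1 and section 11, and reconcile the 2-24 hour rescue definition in 9.2 with the pre-2-hour rule. These are analysis changes only; the rescue instructions to subjects are untouched.

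The cost is SAP text, a programming flag and one table. The eDiary holds rescue date and time, but 9.2 also accepts rescue reported outside it, so a rule is needed for records without a usable time. Response proportions fall slightly in any arm with early rescue. If the planned rates are post-exclusion rates, power may also fall, by little at equal shares and by more if early rescue is commoner on DFN-15, as shown in the working.
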